9.0 Outcome Measures

9.1 Primary Outcome Assessment

9.1.1 Brief Pain Inventory

The Brief Pain Inventory (BPI) is a 17-item patient self-rating scale that assessed sensory and reactive components of pain.⁶⁹ For sensory components, it addresses severity, location, chronicity, and degree of relief due to therapy. For reactive components, it assesses depression, suffering, and perceived availability of relief. Reliability has been demonstrated over short intervals using test retest item correlation; worst pain, $r=0.93$, usual pain, $r=0.78$, pain now $r=0.59$. It has been validated in patients with both cancer and non-cancer pain.^{76,77} Ratings of pain interference with various activities increased as ratings of pain severity were higher. The proportion of patients receiving opioid analgesics also increased with increased severity rating.

The BPI uses 0 to 10 numeric rating scales for item rating because of its simplicity and lack of ambiguity. Since pain can be variable over a day, the BPI asks patients to rate their pain at the time of completing the questionnaire, and also at its worst, least, and average over the previous 24 hours. The primary endpoint for this clinical trial will be based on the 24-hour average pain as reported on the BPI. The ratings can be combined to give a composite index of pain severity. Also, using numeric 0 to 10 scales, with 0 being “no interference” and 10 being “interferes completely”, the BPI asks for ratings of the degree to which pain interferes with mood, walking and other physical activity, works, social activity, relations with others, and sleep. The mean of these scores can be used as a pain interference score.

9.2 Secondary Outcome Assessments

9.2.1 Pressure Pain Threshold

Most QST will be performed using the MAST System. The MAST System is a wireless QST platform featuring a control computer, a touch screen for patient feedback, and an automated pressure actuator. Forces are delivered by a 1-cm² conformal-rubber probe attached to a cylindrical transducer driven by a miniature servo-motor and housed within a polyurethane case that is held comfortably in either hand. Load-cells measure each applied force while a closed-looped control system monitors and adjusts motor output ensuring accurate pressure delivery. All subjects will undergo bilateral pressure pain testing (PPT) at the thumbnail.⁵² The thumbnail was chosen as a neutral, pain-free site remote from the area of surgery. Increased pain sensitivity at the thumbnail (i.e., secondary hyperalgesia) suggests a state of widespread hyperalgesia that may be indicative of centralized pain.^{47,51,54,108} Subjects will undergo testing bilaterally to determine the effect, if any, of prior breast and axillary surgery on thumbnail pressure sensitivity. Testing will be counter-balanced between left and right thumbs. The MAST System will first deliver an ascending series of pressures (5-s duration; 4 kg/cm²/s) at 25-s intervals, beginning at 0.25 kg/cm² and increasing in 0.25 – 0.50 kg/cm² intervals up to tolerance or to a maximum of 10 kg/cm² to the thumbnail. Pain intensity will be rated after each stimulus on a 0-100 numerical rating scale (NRS), with “0” representing “no pain” and “100” representing “extreme pain”. Patient responses obtained in the ascending series will be used to compute a set of 5-7 stimuli between that patient’s threshold and tolerance. These stimuli will then be delivered and rated 3 times each (5-s duration; 25-s inter-stimulus interval) in randomized order. These ratings will be used to compute a psychophysical function of each subject’s pain sensitivity with pressure intensity and response magnitude represented on the x- and y-

axes, respectively. These curves will be used to compare single subject and group changes in pain sensitivity longitudinally throughout the project. Pressure pain threshold and tolerance levels will also be calculated for each subject at each thumbnail.

Because we are aware that the presence of peripheral neuropathy could influence the results of PPT threshold in the thumb, we will also test this at another site not affected by peripheral neuropathy: the deltoid muscle. The inclusion of this particular site was based on recent evidence showing that pressure pain threshold was bilaterally reduced at the deltoid muscle in BCS compared to healthy controls, and that pressure pain threshold at the affected deltoid was negatively correlated to neck pain intensity.⁵⁴ Testing will be conducted using a 1 cm² rubber probe attached to a digital algometer. Test order will be counter-balanced between affected and non-affected sides. Pressure will be manually increased at a rate of 0.3 kg/cm²/s to a maximum 10 kg following an ascending method of limits. Subjects will indicate the point at which the pressure sensation becomes painful (pressure pain threshold) and the point in which the pain becomes intolerable (pressure pain tolerance). A tolerance of 10 kg/cm² will be used for patients that fail to press the button before test completion. Measurements will be conducted 3 times at each side (20-60 second inter-stimulus interval) with mean values used for analysis.

9.2.2 Conditioned Pain Modulation (CPM)

Endogenous pain modulation will be evaluated using a CPM paradigm.⁶³ CPM procedures incorporate a conditioning stimulus (a noxious stimulus that activates pain modulatory systems) and a test stimulus (a noxious stimulus used to evaluate the analgesic response to the conditioning stimulus). In this study, painful pressure stimuli will be delivered via two MAST actuators positioned on opposite thumbs with pressure at one thumb serving as the test stimulus and pressure at the other thumb serving as the conditioning stimulus. The test stimulus will be applied continuously for 30-s to the thumbnail of the affected side at an intensity that induces a moderate level of pain for that patient (i.e., a rating of 30-50/100). Patients will rate the intensity of the pressure at 10-, 20-, and 30-s on a NRS. CPM will be induced 5-min later by applying 60-s of continuous pressure to the thumbnail of the non-affected side at the same pain intensity as the test stimulus. CPM magnitude will be calculated as the difference in mean pain rating to the test-stimulus applied prior to and during the conditioning stimulus. Previous work by our group and others demonstrated this to be a valid method of CPM assessment in patients with chronic pain.^{55-57,60,63-66}

9.3 Patient-Reported Outcome Assessments

All enrolled subjects and controls will complete the battery of questionnaires described above, which will take approximately 1 hour to complete. All questionnaires that assess self-reported pain will be completed prior to QST; the remainder will be completed between PPT and CPM assessment.

Measures of centralization of pain

- The **Michigan Body Map and Symptom Severity Scale**, a modified version of the Wolfe Regional Pain Scale, will be used to quantify (a) the locations of breast cancer treatment-related pain using a checklist that allows for efficient scoring and (b) the severity of key symptoms, including fatigue, sleep disturbance, and cognitive function. Measures of pain distribution and the presence of this symptom cluster have been repeatedly found to be associated with centrally-mediated pain symptoms.⁷⁸⁻⁸⁰
- Qualitative Pain Characteristics. **PainDETECT**⁷⁰ is a 9-item measure of sensory descriptors, spatial, and temporal characteristics that has been shown to identify neuropathic components of pain in low back pain and in osteoarthritis.³⁴ It distinguishes neuropathic from musculoskeletal pain.
- Treatment-related toxicity. **The FACT/GOG-NTX** neurotoxicity module is an 11-item subscale specifically developed to address chemotherapy-associated peripheral neurotoxicity and its consequences on functional status.⁷¹ The subscale scores correlate with objective neuropathy measures, specifically pin sensibility, strength, and deep tendon reflexes.

- Functional status, sleep, and fatigue. The following **PROMIS** short-forms will be used in this study: **Fatigue, Sleep Disturbance, and Physical Function**.⁶⁸ The 7-item Fatigue scale assesses the experience of fatigue as well as its impact on physical, mental, and social activities. The 8-item Sleep Disturbance scale assesses perceptions of sleep quality, sleep depth, and restoration associated with sleep. The 10-item Physical Function scale assesses self-reported function, including the ability to perform activities of daily living. The PROMIS scales possess favorable reliability and enhanced precision with lowered patient burden when compared to comparable legacy assessment instruments.
- Psychiatric status. The **Hospital Anxiety and Depression Scale (HADS)** will be used to assess anxiety and depressive symptoms.⁸¹ The HADS is a 14 item questionnaire that has been extensively evaluated for the assessment of mood disorders in patients with cancer.^{93,94}
- Cognitive dysfunction. The 38-item **Multiple Abilities Self-Report Questionnaire (MASQ)**,^{55,95,96} is comprised of five cognitive domains: language ability, visuo-perceptual ability, verbal memory, visual memory, and attention/concentration. Satisfactory reliability and validity have been demonstrated.^{72,82,83}

10.0 Safety Assessments

Patients must be seen by an appropriately trained health professional at every visit and the evaluation must be documented. The procedures discussed in section 9.0 will be performed at the designated visits.

10.1 Adverse Events

An AE is any untoward medical occurrence in a patient or clinical investigation subject administered a pharmaceutical product and which does not necessarily have to have a causal relationship with this treatment.

An AE, therefore, can be any unfavorable and unintended sign (including an abnormal laboratory finding, for example), symptom, or disease temporally associated with the use of a medicinal product, whether or not considered related to the medicinal product.

Examples of AEs are as follows:

- Changes in the general condition of the patient
- Subjective symptoms offered by or elicited from the patient
- Objective signs observed by the Investigator or other study personnel
- All concurrent diseases that occur after the start of the study, including any change in severity or frequency of preexisting disease
- All clinically relevant abnormalities in laboratory values or clinically relevant physical findings that occur during the study

In general, AE reporting for this clinical trial will follow the University of Michigan IRBMED guidelines. However, changes in the pain or occurrence of symptoms noted in the patient's baseline self-report questionnaires will not be recorded as AEs. In addition, if patients are undergoing treatment with anticancer agents such as aromatase inhibitors, tamoxifen, bisphosphonates, and/or trastuzumab, expected side effects of these medications will not be reported to the IRB. Changes that are clinically significant, as assessed by the Investigator, or that qualify as serious will be reported as **SAEs**.

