- Treatment-related toxicity. The FACT/GOG-NTX neurotoxicity module is an 11-item subscale specifically developed to address chemotherapy-associated peripheral neurotoxicity and its consequences on functional status.⁷¹ The subscale scores correlate with objective neuropathy measures, specifically pin sensibility, strength, and deep tendon reflexes.
- Functional status, sleep, and fatigue. The following PROMIS short-forms will be used in this study: Fatigue, Sleep Disturbance, and Physical Function.⁶⁸ The 7-item Fatigue scale assesses the experience of fatigue as well as its impact on physical, mental, and social activities. The 8-item Sleep Disturbance scale assesses perceptions of sleep quality, sleep depth, and restoration associated with sleep. The 10-item Physical Function scale assesses self-reported function, including the ability to perform activities of daily living. The PROMIS scales possess favorable reliability and enhanced precision with lowered patient burden when compared to comparable legacy assessment instruments.
- Psychiatric status. The Hospital Anxiety and Depression Scale (HADS) will be used to assess anxiety and depressive symptoms.⁸¹ The HADS is a 14 item questionnaire that has been extensively evaluated for the assessment of mood disorders in patients with cancer.^{93,94}
- Cognitive dysfunction. The 38-item Multiple Abilities Self-Report Questionnaire (MASQ),^{55,95,96} is comprised of five cognitive domains: language ability, visuo-perceptual ability, verbal memory, visual memory, and attention/concentration. Satisfactory reliability and validity have been demonstrated.^{72,82,83}

Treatment of Chronic Pain

Many different kinds of medications are used in the treatment of chronic pain states such as fibromyalgia and irritable bowel syndrome; these medications have had varying degrees of success.⁸⁴⁻⁸⁶ Although antidepressants are the cornerstone of many treatment paradigms, other types of agents such as anticonvulsants, antispasticity agents, anxiolytics, sedatives, and opiates are also used. Many patients with chronic pain use NSAIDs and acetaminophen⁸⁷ even though peripheral inflammation has not been demonstrated,⁸⁸ and numerous studies have failed to confirm the efficacy of these analgesics in the treatment of fibromyalgia.⁸⁹⁻⁹³ These agents do, however, provide an element of protection against other peripheral pain generators such as osteoarthritis.

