- Schedule an appointment for the patient to return in 5 weeks. This visit may be scheduled up to 4 days early.

Section 9.0 provides a detailed description of each outcome assessment.

Post-Treatment Evaluation (Visit 2)

Post-Treatment Evaluation (Visit 2) will be conducted 5 weeks after Baseline (Visit 1) to complete endpoint assessments. At this visit, patients will be given 1 prescription bottle containing the dose de-escalation for 14 days. *Visit 2 can be performed up to 4 days early (should be conducted during week 4 of full-dose treatment).*

At Post-Treatment Evaluation (Visit 2) the following procedures will be completed:

- Assess patient tolerance of medication and record AEs
- Inquire as to any change in physical symptoms, sleep, and/or mood (to include suicidal ideation)
- Record concomitant medications/therapies on concomitant medication form
- Measure vital signs and record values
- Collect study drug from the previous visit and perform drug accountability. If the subject has pills remaining, either because she missed a pill or because this visit was conducted early, the pills should not be returned to the subject.
- Complete the following outcome assessments:
 - Evaluation of pressure pain threshold
 - Patient-reported outcome assessments:
 - Brief Pain Inventory (BPI)
 - Michigan Body Map and Symptom Severity Scale

- PainDETECT
- FACT/GOG-NTX subscale
- o Evaluation of CPM
- o Patient-reported outcome assessments
 - PROMIS (Fatigue-SF)
 - PROMIS (Sleep Disturbance-SF)
 - PROMIS (Physical Function-SF)
 - Hospital Anxiety and Depression Scale (HADS)
 - Multiple Ability Self-Report Questionnaire (MASQ)
- Dispense the prescription bottle containing study drug for the dose de-escalation (2 weeks) and review dosing instructions.
 - For those patients who wish to continue to take commercially-available duloxetine after study completion, the patient can transition directly to duloxetine 60 mg daily using a prescription provided by her PCP or other treating physician, and she does not need to taper off and then restart drug. If she does not yet have the prescription, she will be given the two week supply of dose de-escalation study drug. Once she obtains the medication from her pharmacy she can stop the 30 mg dose and start the commercial supply.

Section 9.0 provides a detailed description of each outcome assessment.

Final Evaluation (Phone visit)

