10.3 Severity Assessment

The Investigator will provide an assessment of the severity of each AE. *Severity*, which is a description of the intensity of manifestation of the AE, is distinct from *seriousness*, which implies a patient outcome or AE-required treatment measure associated with a threat to life or functionality. Severity of AEs will be graded according to CTCAE criteria, version 4.

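### Section 10.1 contradicts its own AE definition and Section 10.3: non-serious worsening of baseline symptoms may go unrecorded, and non-serious changes may be reported as SAEs

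*Combined protocol and SAP*

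**What the plan says.** Section 10.1 opens with a broad definition. Its examples of AEs include "Subjective symptoms offered by or elicited from the patient" and concurrent diseases arising after study start, "including any change in severity or frequency of preexisting disease".

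The last paragraph of the section refers to institutional guidelines in general and then makes an exception: "changes in the pain or occurrence of symptoms noted in the patient's baseline self-report questionnaires will not be recorded as AEs". The operative words, "baseline self-report questionnaires will not be recorded as AEs", carry no severity limit. A sentence on expected side effects of anticancer drugs follows; those are not reported to the IRB. The paragraph ends: "Changes that are clinically significant, as assessed by the Investigator, or that qualify as serious will be reported as" SAEs.

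Section 10.3 says that severity and seriousness are different things. It describes seriousness as something "which implies a patient outcome or AE-required treatment measure associated with a threat to life or functionality", and grades the severity of each AE by CTCAE version 4.

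The baseline battery is wide. Section 2.0 states: "The following PROMIS short-forms will be used in this study: Fatigue, Sleep Disturbance, and Physical Function". Sections 8.2 and 9.3 add anxiety and depression (HADS), cognition (MASQ), neuropathy (FACT/GOG-NTX), neuropathic pain (PainDETECT) and the body map with its symptom severity scale. At Visit 2 and the final phone evaluation, Section 8.2 tells staff to record AEs and also to "Inquire as to any change in physical symptoms, sleep, and/or mood (to include suicidal ideation").

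**The concern.** The definition and the exemption give different answers for the same event, and the closing sentence sets an SAE threshold that Section 10.3 does not support. A coordinator who hears at Visit 2 that a patient's sleep or mood is worse than at baseline cannot tell from the text whether to record nothing, an AE or an SAE.

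The affected group is unlikely to be small. Section 2.0 calls fatigue, sleep, cognitive and mood symptoms common in survivors. Section 4.0 says that a high proportion of survivors with chronic pain need an antidepressant or anxiolytic, and inclusion criterion 7 requires willingness to stop SSRIs and tricyclics before treatment. Many cases may therefore enter with these symptoms noted.

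What is at stake is the safety record. Sections 10.2 and 10.3 attach causality and grade to AEs, so an event that is not recorded gets neither. Section 13.0 relies on adverse-event monitoring. With one treated arm, no concurrent treated comparator would show up under-recording.

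**Working it through.** No arithmetic applies. The plan states no AE or SAE rate, so there is no figure to reproduce. The check is to follow typical events through the text.

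Two readings of the exemption are possible, because *changes* attaches to pain and *occurrence* attaches to the other symptoms:

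- Reading A: a symptom noted at baseline is exempt, including when it worsens.
- Reading B: only the continued presence of a non-pain symptom is exempt; its worsening stays under the general definition.

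| Event in a case | Reading A | Reading B | General definition in 10.1 with seriousness as in 10.3 |
|---|---|---|---|
| Symptom absent at baseline, non-serious | AE | AE | AE |
| Non-pain baseline symptom worsens, not clinically significant | Not recorded | AE | AE |
| Non-pain baseline symptom worsens, clinically significant, not serious | SAE | SAE | AE |
| Pain worsens, not clinically significant | Not recorded | Not recorded | AE |
| Pain worsens, clinically significant, not serious | SAE | SAE | AE |
| Change that is serious | SAE | SAE | SAE |

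The SAE entries for non-serious events come from the *or* in the closing sentence, which makes clinical significance sufficient on its own. They assume that the sentence covers the symptoms exempted earlier in the paragraph. If it covers only the anticancer-drug effects in the sentence just before it, row 3 becomes not recorded under A and AE under B, and row 5 becomes not recorded under both.

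Three results follow:

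1. Under A, row 2 conflicts with the section's own definition. Row 4 does so under both readings.
2. Rows 3 and 5 conflict with Section 10.3 under both readings, if the closing sentence covers these symptoms.
3. Where the columns differ from the last one, an AE becomes either no record or an SAE. That gives the direction of error. Its size would need the share of cases with each symptom at baseline and the frequency of worsening, and the documents give neither.

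Section 6.5 acts on graded toxicities attributed to study drug. It does not say that a symptom must first be recorded as an AE under Section 10.1, so it is not blocked. The text does not say how it applies to a symptom that is exempt from recording.

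**The case against.** The strongest reply is Reading B: the drafters meant only that a symptom already present need not be entered again, and worsening remains an ordinary AE. That is a natural reading. A reader might infer that baseline symptoms have no ordinary AE category at all; the text does not establish that for non-pain symptoms. What stands is that A is equally open, so staff could classify the same event differently. Reading B also leaves the pain exemption and the SAE sentence as they are. Keeping pain, the trial's endpoint, out of AE records can be defended, but then it should be a stated exception to the definition.

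A reader might also infer that answers to the sleep and mood questions are simply lost. That goes too far. New symptoms are AEs on any reading, and staff are told to record AEs at both contacts.

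Third, fatigue, sleep, function, mood, cognition and neuropathy are secondary outcomes in Section 11, so worsening is measured. This reduces the loss but does not remove it. Score changes carry no causality or CTCAE grade. Section 8.0 schedules questionnaires only at Visits 1 and 2. Under Section 5.7, patients who stop during the 1-week or 2-week supply have a phone visit, and Section 8.2 leaves outcome assessment at early termination to the investigator. First-week intolerance and the taper period are therefore the least covered.

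Finally, the institutional guidelines are not reproduced and may define SAEs properly. That cannot be checked, and the exemption is written as a departure from them.

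**Conclusion.** The point holds as a contradiction in the reporting rules: within Section 10.1 on what counts as an AE, and between Sections 10.1 and 10.3 on what counts as serious. The under-recording of non-pain symptoms rests on Reading A. The inflated SAE reporting rests on the closing sentence covering the exempted symptoms. On those assumptions, non-serious worsening is under-recorded and SAE reports include non-serious events.

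The size cannot be stated. A reader might infer that both AE and SAE rates are bound to be wrong, or that worsening would be reported as 0 of 84 cases. The documents do not support either. Section 11 plans no AE-rate analysis. A count of zero would require every affected patient to have had that symptom noted at baseline and every worsening to be dropped, yet the same paragraph sends some of those changes to SAE reporting. The consequence is for safety monitoring and any tolerability report; the efficacy outcomes are not affected. This should be corrected.

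**What to change.** Amend Sections 10.1 and 8.2 as follows:

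1. Replace the exemption with this rule: a symptom present at baseline is recorded as an AE when its CTCAE v4 grade rises above its baseline grade. If the sponsor wishes to leave pain out, say so as an explicit exception and give the reason.
2. State that the baseline AE record at Visit 1 includes a CTCAE grade for symptoms noted in the questionnaires. This is needed because Section 10.3 grades only AEs, so a symptom that appears only in a questionnaire may otherwise have no reference grade.
3. Limit SAE reporting to events that meet seriousness criteria, and record clinically significant non-serious changes as AEs. Keep the sentence on anticancer-drug side effects separate, so that it is clear what the reporting rule covers.
4. Reconcile Section 6.5 with this wording, without changing its treatment rule.

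The cost is a protocol amendment, grading of questionnaire-noted symptoms at Visit 1, and some additional AE entries. No visit, instrument or treatment rule changes.
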